5.3. Lifestyle Considerations

All study participants should be instructed not to donate blood or blood products during the study or for 6 months after the last dose of the study intervention.

Reproductive and Contraceptive guidance is provided in Section [10.4](#), Appendix 4.

5.4. Screen Failures

Screen failures are defined as participants who consent to participate in the clinical study but are not subsequently enrolled in the study. A minimal set of screen failure information is required to ensure transparent reporting of screen failure participants to meet the Consolidated Standards of Reporting Trials (CONSORT) publishing requirements and to respond to queries from regulatory authorities. Minimal information includes demography, screen failure details, eligibility criteria, and any SAE.

Individuals who do not meet the criteria for participation in this study (screen failure) may be rescreened only once for failure due to any of the following criteria: 2, 8, 21, 22, 23, 26, 34, or 35. Individuals who failed criterion 25 can be rescreened once if appropriate treatment for LTBI is underway. Rescreened participants should be assigned a new participant number. Each time rescreening is performed, the individual must sign a new ICF.

6. Study Intervention

Study intervention is defined as any investigational intervention(s), marketed product(s), placebo, or medical device(s) intended to be administered to/used by a study participant according to the study protocol.

6.1. Study Intervention(s) Administered

Study interventions

Each participant will receive multiple IV infusions of placebo, LY3462817 300 mg, or LY3462817 700 mg.

Intervention Name	Placebo	LY3462817	LY3462817	
Dose Formulation	0.9% sodium chloride solution	Solution	Solution	
Unit Dose Strengths	-	50 mg/mL in a 3-mL vial		
Dosage Level(s) (mg)	Not applicable	300	700	
Use	Placebo	Experimental		
IMP and NIMP	IMP	IMP		
Sourcing	Commercially available 0.9% sodium chloride solution sourced centrally by Lilly	From Lilly		
Packaging and Labeling	Commercially available 0.9% sodium chloride solution	Study intervention will be provided in glass vials and will be labeled as required per country requirement		

Abbreviations: IMP = Investigational Medicinal Product; NIMP = Noninvestigational Medicinal Product.

Study intervention will be prepared by an unblinded pharmacy staff or pharmacist who is not involved in any other study-related procedures.

The study intervention is planned to be administered as an IV infusion.

The infusion rate may be reduced as deemed necessary if an infusion reaction is observed (Section 8.3.6). Participants will be monitored for signs and symptoms of infusion reaction:

- during the infusion, and
- for at least 1 hour after completion of the infusion.

Infusion information may be found in the pharmacy binder.

Resuscitation equipment, emergency drugs, and appropriately trained medical staff must be available during the infusion and for at least 1 hour after the completion of the infusion.

6.2. Preparation/Handling/Storage/Accountability

The investigator or designee must confirm appropriate storage conditions have been maintained during transit for all study intervention received and any discrepancies are reported and resolved before use of the study intervention.

Only participants enrolled in the study may receive study intervention and only authorized study staff or designee may supply or administer study intervention. All study intervention must be stored in a secure, environmentally controlled, and monitored (manual or automated) area in accordance with the labeled storage conditions with access limited to the investigator and authorized study staff or designee.

The investigator, institution, or the head of the medical institution (where applicable) is responsible for study intervention accountability, reconciliation, and record maintenance (i.e., receipt, reconciliation, and final disposition records).

Further guidance and information for the final disposition of unused study interventions are provided in the pharmacy manual.

6.3. Measures to Minimize Bias: Randomization and Blinding

To preserve the blinding of the study, a minimum number of Lilly personnel who are not directly involved with investigational sites will see the randomization table and treatment assignments before the study is complete.

Joint, disease activity, and safety assessments

Joint Assessor

To prevent potential bias due to observed efficacy or laboratory changes, a “dual assessor” approach will be used to evaluate efficacy and safety. The Joint Assessor (or designee) should be a rheumatologist or skilled arthritis assessor. The Joint Assessor will be responsible for completing the joint counts. To ensure consistent joint evaluation throughout the trial, individual participants should be evaluated by the same Joint Assessor for all study visits. The Joint Assessor must not access or discuss with the participant the patient-reported assessments, Physician’s Global Assessment of Disease Activity (PhGADA_VAS), and safety assessments.

Safety Assessor

The Safety Assessor (or designee) should be a rheumatologist (or medically qualified physician) and will have access to both safety and efficacy data. The Safety Assessor may be the principal investigator. The Safety Assessor will be responsible for completing the PhGADA_VAS. To ensure consistent PhGADA_VAS throughout the trial, the instrument should be evaluated by the same physician at all study visits. The Safety Assessor will have access to source documents, laboratory results, and electronic case report forms (eCRFs) and will be responsible for making treatment decisions based on a participant’s clinical response and laboratory parameters.

Method of treatment assignment

Assignment to treatment groups will be determined by a computer-generated random sequence using an interactive web-response system (IWRS).

Participants will be stratified by prior use of csDMARD only or by tsDMARD/bDMARDs use (yes versus no).

Emergency unblinding

In case of an emergency, the investigator has the sole responsibility for determining if unblinding of a participant's treatment assignment is warranted. Participant safety must always be the first consideration in making such a determination. If a participant's treatment assignment is unblinded, the sponsor must be notified immediately.

Emergency unblinding for AEs may be performed through the IWRs. This option may be used ONLY if the participant's well-being requires knowledge of the participant's treatment assignment. All calls resulting in an unblinding event are recorded and reported by the IWRs.

6.4. Study Intervention Compliance

Study intervention will be administered under medical supervision by the investigator or designee. The date and time of each dose administered will be recorded in the source documents and in the case report form (CRF). The dose of study intervention and study participant identification will be confirmed prior to the time of dosing.

6.5. Concomitant Therapy

Participants will be instructed to consult the investigator or other appropriate study personnel at the site before taking any new medications or supplements during the study.

Additional drugs are to be avoided during the study unless required to treat an AE or for the treatment of an ongoing medical condition. Investigators should follow local guidelines for the management of lipid disorders. If the need for other concomitant medications arises, discontinuation of the participant from study intervention or the study will be at the discretion of the investigator in consultation with sponsor (or designee).

All medications, whether prescription or over-the-counter, used at screening and/or during the study must be documented in the eCRF with start and stop dates.

6.5.1. Permitted Rheumatoid Arthritis Concomitant Therapy

Treatment with the following concomitant medications for RA during the study are permitted as outlined below and in the inclusion/exclusion criteria. This applies to all participants during Period 1 and any participant that remains on LY3462817 during Period 2.

Concomitant therapy	Permitted	Not permitted
Methotrexate (MTX)	If parenteral, up to 20 mg/week If oral, up to 25 mg/week Subjects on MTX should receive supplementation with folic acid according to local standard of care	
Hydroxychloroquine	up to 400 mg/day	
Oral sulfasalazine	up to 3000 mg/day	

Concomitant therapy	Permitted	Not permitted
Leflunomide	up to 20 mg/day	
Nonsteroidal anti-inflammatory drugs (NSAIDs)	Permitted during the Period 1 only if the participant was on a stable dose for at least 7 days before planned randomization.	Increase of NSAID dose and/or introduction of new NSAIDs are not permitted during the Period 1 or in participants receiving LY3462817 in Period 2
Analgesics	Dose reductions and/or termination of analgesics are permitted at any time.	
Corticosteroids	
Prednisone (or equivalent) at doses up to 10 mg per day is allowed during this study but must be maintained at stable levels from ≥ 4 weeks prior to the screening magnetic resonance imaging (MRI) through Period 1 or in participants receiving LY3462817 in Period 2.
 
Topical, intranasal, intraocular, and inhaled corticosteroids are permitted.
 
Directions for use of intra-articular glucocorticoids:
 
If an unforeseen intra-articular glucocorticoid injection is required during the study, it will be noted as a protocol deviation.
 
Any joints that had been injected with intra-articular corticosteroids within 42 days prior to the screening MRI will be censored from the clinician-administered Tender Joint Counts (TJCs) and Swollen Joint Counts (SJC) (68/66) for the duration of the study.
	
Participants who were not previously on prednisone (or equivalent) prior to randomization should not initiate corticosteroid therapy during the study during Period 1 or in participants receiving LY3462817 in Period 2.
 
Participants should not receive other systemic corticosteroids during the study including intra-muscular or intra-articular corticosteroids during Period 1 or in participants receiving LY3462817 in Period 2.

Folic acid	Local standard of care should be followed for concomitant administration of folic acid.	

6.5.2. Prohibited Concomitant Therapy

Live vaccinations are not allowed up to 3 months prior to screening or at any time during the study. Live herpes zoster vaccination is not permitted within 30 days of planned randomization or at any time during the study.

Nonlive seasonal vaccinations and/or emergency vaccination, such as rabies or tetanus vaccinations, are allowed.

6.5.3. Standard of Care Therapy after Week 14

All placebo patients should begin SOC therapy at Week 14 at the investigator's discretion.

Participants randomized to LY3462817 at baseline and not achieving low disease activity (CDAI ≤ 10) at Week 14 will no longer receive study drug infusions and should receive SOC therapy at the investigator's discretion.

Participants who achieve low disease activity at Week 14, and maintain treatment with LY3462817 during Period 2, can be switched to SOC prior to Week 24 if the participant stops receiving clinical benefit. Name(s) and dosage regimen(s) must be recorded for the SOC therapy. Standard of care medications will not be supplied by the sponsor.

6.6. Dose Modification

Dose modifications during the treatment period will not be allowed.

6.7. Intervention after the End of the Study

No continued access is planned after completion of this study, as additional efficacy would be needed to demonstrate continued access criteria.

7. Discontinuation of Study Intervention and Participant Discontinuation/Withdrawal

The sections below describe reasons for a participant's

- temporary or permanent discontinuation of study intervention (Section 7.1), or
- discontinuation (withdrawal) from the study (Section 7.2).

Discontinuation of specific sites or of the trial as a whole are handled as part of regulatory, ethical, and trial oversight considerations in Section 10.1, Appendix 1.

7.1. Discontinuation of Study Intervention

Study intervention may be temporarily withheld or permanently discontinued during the study.

Participants who permanently discontinue study intervention early will undergo early termination procedures, which include an early termination visit and a posttreatment follow-up visit (V801) as described in the SoA (Section 1.3).

The investigator will complete any AE reporting and follow-up (Section 8.3).

7.1.1. Criteria for Temporary Interruption (Withholding) of Study Intervention

Study treatment may be temporarily discontinued if the participant requires surgery.

Administration of the study intervention may be restarted only after adequate wound healing.

This and other situations that may merit temporary discontinuation of the study intervention should be discussed with the sponsor. The investigator should consult with the Medical Monitor and then determine when it is appropriate to recommence study treatment.

7.1.1.1. Infection-related Criteria for Temporary Withholding of Study Intervention

Study intervention will be temporarily withheld if any of the following infection-related criteria occur during the study:

1. Serious or opportunistic infections, as defined in Exclusion Criteria (Section 5.2). Study intervention can be withheld until resolution of all acute clinical signs and symptoms, and completion of all appropriate anti-infective treatment (exception for LTBI, noted below). The investigator should consult with the Medical Monitor and then determine when it is appropriate to recommence study treatment.
2. If a participant is diagnosed with LTBI during the study and is treated for LTBI as follows:
 - a) Study intervention is temporarily held for at least the first 4 weeks of LTBI treatment.
 - b) If there is no evidence of hepatotoxicity (ALT/AST must remain ≤ 2 times ULN) or other treatment intolerance after receiving at least 4 weeks of appropriate LTBI therapy (as per WHO and/or CDC guidelines), then study intervention may be resumed.
 - c) The participant must complete appropriate LTBI therapy during the course of the study to remain eligible to continue to receive study intervention.
3. HBV DNA results reported as positive, or as detecting HBV DNA, but HBV DNA is below the level of quantification. The Medical Monitor should be contacted regarding study status

of the participant. Hepatitis B virus DNA testing should be repeated as soon as possible. If HBV DNA is confirmed positive, then study intervention should be discontinued.

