8.2.7. Hepatitis B Testing and Monitoring

Initial testing for HBV infection includes hepatitis B surface antigen (HBsAg) and hepatitis B core antibody (anti-HBc).

If...	Then...
If HBsAg is positive	the participant is excluded
If HBsAg is negative and anti-HBc is negative	the participant is not excluded
If HBsAg is negative and anti-HBc is positive	further testing for HBV DNA is required
If the screening HBV DNA is positive	the participant is excluded (see Section 5.2)

Participants who are hepatitis B core antibody-positive and HBV DNA-negative (undetectable) at Visit 1 are not excluded but will require HBV DNA monitoring every 3 months and at the participant's last visit.

The following actions should be taken in response to HBV DNA test results.

If...	Then...
If a single result is obtained with a value "below limit of quantitation"	the test should be repeated within approximately 2 weeks
If the repeat test result is "target not detected"	monitoring may resume according to the study schedule
If the participant has 2 or more test results with a value "below limit of quantitation" during the study	HBV DNA testing should be performed approximately once per month for the remainder of the study and referral to a hepatologist is recommended
If a result is obtained with a value "above limit of quantitation" at any time during the study	the participant will be permanently discontinued from the study intervention (see Section 7.1) and should be referred to a hepatology specialist immediately. In selected cases, investigators may temporarily continue study intervention in accordance with current immunomodulator management in the setting of HBV DNA positivity. This option may be considered in

If...	Then...
	consultation with the sponsor (or its designee) and after evaluation of individual participant's risks and benefits.

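### Protocol Sections 7.1.1.1, 7.1.2 and 8.2.7 are not aligned on study drug when HBV DNA is detected but below quantification

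*Protocol*

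**What the plan says.** Three places in the protocol deal with HBV DNA found during the study.

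**Section 7.1.1.1** opens with a mandatory hold: "Study intervention will be temporarily withheld if any of the following infection-related criteria occur during the study". Item 3 gives the trigger: "HBV DNA results reported as positive, or as detecting HBV DNA, but HBV DNA is below the level of quantification". The Medical Monitor is contacted about the participant's status, and "Hepatitis B virus DNA testing should be repeated as soon as possible". The item closes: "If HBV DNA is confirmed positive, then study intervention should be discontinued".

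**Section 8.2.7** has a table of actions keyed to HBV DNA results. For a single result below the limit of quantitation, "the test should be repeated within approximately 2 weeks". If the repeat finds no target, "monitoring may resume according to the study schedule". After two or more below-limit results, "HBV DNA testing should be performed approximately once per month for the remainder of the study and referral to a hepatologist is recommended". A result above the limit leads to permanent discontinuation of study drug and immediate specialist referral. In selected cases the investigator may temporarily continue, in consultation with the sponsor.

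**Section 7.1.2** names a positive HBV DNA among infections that may merit permanent discontinuation in the investigator's opinion, with specialist evaluation before stopping. It refers the reader to 8.2.7.

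**The concern.** Anti-HBc-positive participants whose HBV DNA is undetectable at screening may enroll, so the protocol needs one clear rule for HBV DNA that later becomes detectable under an immunomodulator. It has two partial rules that start from the same laboratory result and do not refer to each other at that point. One is a hold followed by a possible stop. The other is a testing and referral pathway in which the only row with a study-drug action is the one for quantifiable virus.

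What is at stake is participant protection and consistent conduct. Two sites with the same result could act differently, depending on which section they open.

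**Working it through.** The plan gives no figure to reproduce, and the point depends on no alpha, effect size or standard deviation. The check is a comparison by result, followed by a count of the infusions and participants it can reach.

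| Result | Section 7.1.1.1 item 3 | Section 8.2.7 table |
|---|---|---|
| First detected, unquantifiable | Withhold; contact Medical Monitor; repeat as soon as possible | Repeat in about 2 weeks; silent on dosing |
| Repeat negative | No restart condition | Monitoring may resume; silent on dosing |
| Second detected, unquantifiable | Discontinue, if this counts as confirmed positive | Monthly tests, referral recommended; silent on dosing |
| Above the limit | Not addressed separately | Discontinue permanently; temporary continuation possible in selected cases |

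Four things follow.

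1. **The table is more than a test schedule.** It is introduced as the actions that results call for, and one row does state a study-drug action. A site may take the absence of any hold or stop in the other rows to mean that none is required.
2. **The stated actions are not graded consistently.** If a repeat below-limit result confirms positivity, 7.1.1.1 discontinues without exception, while 8.2.7 allows an exception above the limit. The lower viral load can then carry the stricter rule. This comparison uses only what each section states.
3. **The cross-references do not join the rules.** Section 7.1.2 sends the reader to 8.2.7. Only the above-limit row of 8.2.7 points back to Section 7.1. Item 3 of 7.1.1.1 does not cite 8.2.7.
4. **Restarting is open.** Items 1 and 2 of 7.1.1.1 address recommencing study drug; item 3 does not.

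**Infusions in reach.** The Schedule of Activities places HBV DNA at screening, Week 12, Week 24, early termination and the last visit. Infusions are at baseline and Weeks 4, 8, 12, 16, 20 and 24. Assuming the Week 12 result is not back before the Week 12 infusion, the first dose it can decide is Week 16. A repeat 2 weeks after that sample falls at about Week 12 + 2 = 14, also before Week 16. At most three infusions are in play from scheduled testing: Weeks 16, 20 and 24. Week 24 is the last dosing visit, so its sample decides no later dose.

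**Participants in reach.** The documents give no anti-HBc prevalence. Assuming 5% to 15%:
- Monitored pool: 0.05 × 80 = 4 to 0.15 × 80 = 12.
- Of these, randomized to LY3462817 (40 + 20 = 60): 0.05 × 60 = 3 to 0.15 × 60 = 9.
- Of these, only participants with CDAI ≤10 at Week 14 are dosed after Week 12, and only those with a detected, unquantifiable result meet the misaligned rules. The documents give neither rate.

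The number affected is therefore a fraction of 3 to 9 under that assumption, and may be zero.

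**The case against.** The best defense is that both sections can be followed together. Section 7.1.1.1 governs holding the drug, and 8.2.7 is headed as testing and monitoring. A site can withhold under the first while it retests and refers under the second. Testing for the rest of the study does not imply dosing, because 7.1.2 encourages participants who stop the drug to remain in the study. A limit of about 2 weeks is compatible with repeating as soon as possible. Contact with the Medical Monitor adds a central check.

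Much of this stands, and it rules out three stronger readings that a reader might infer:

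- *The sections give opposite dosing instructions.* They do not. The below-limit rows of 8.2.7 contain no dosing instruction, and what may resume after a negative repeat is monitoring. Continued dosing is an inference from the contrast with the above-limit row. The discrepancy at the second result also depends on treating a repeat below-limit result as confirmed positive, which is plausible but not defined.
- *Section 7.1.2 makes a positive HBV DNA a mandatory stop.* It leaves the decision to the investigator's opinion.
- *The rule decides which data enter the primary analysis.* The protocol's estimand table covers the double-blind period, and the first scheduled on-treatment HBV DNA sample is at its final visit. A stop triggered by that result cannot remove Week 12 or earlier data. For ACR20, SAP Section 4.4.1.2.1 ties imputation to non-response at Week 12 or discontinuation before it. Only an unscheduled earlier test could reach these analyses. The exploratory Period 2 analyses, which drop observations after discontinuation, can be touched.

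The defense does not supply a link between the sections. The joint reading works only for a site that already knows to open 7.1.1.1. The Medical Monitor contact is itself written only there, so a site using the 8.2.7 below-limit rows is not prompted to make it.

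**Conclusion.** The three sections are not aligned for detectable but unquantifiable HBV DNA, and they should be reconciled. Section 7.1.1.1 holds and then discontinues on an undefined confirmation. Section 8.2.7 gives only testing and referral below the limit and reserves discontinuation, with an exception, for results above it. Section 7.1.2 leaves the matter to judgment and points to the table without the hold. This is more than missing detail, because a site relying on 8.2.7 could continue a participant whom 7.1.1.1 would hold or stop.

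The reach is small: a few anti-HBc-positive participants at most, and mainly three infusions in those continuing LY3462817 in Period 2. That size rests on the assumed 5% to 15% prevalence, on the scheduled test dates, and on the Week 12 result arriving after that visit's infusion. The Week 12 primary analysis is essentially unaffected, and sample size and power are unaffected. The case for correction rests on participant safety and uniform conduct. Nothing here says which clinical rule is right.

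**What to change.** Reconcile Section 7.1.1.1 item 3, Section 7.1.2 and the Section 8.2.7 table into a single action table with three rows: first below-quantification result, repeat below-quantification result, and above-quantification result. Each row should state one study-drug action and one retest interval. Define what makes HBV DNA a confirmed positive, and state the condition for restarting after a negative repeat. Have 7.1.1.1 and 7.1.2 refer to the table instead of restating the rule. The sponsor's clinical team decides which actions are intended.

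The cost is a short protocol amendment and a notice to sites. The reconciliation itself needs no additional participants and no change to the sample size or the primary analysis.

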7.1.2. Criteria for Permanent Discontinuation of Study Intervention

In rare instances, it may be necessary for a participant to permanently discontinue (definitive discontinuation) study intervention. If study intervention is definitively discontinued, the participant will be encouraged to remain in the study. See the SoA for data to be collected at the time of discontinuation of study intervention and follow-up and for any further evaluations that need to be completed.

Permanent discontinuation of study intervention should occur if the scenarios described occur during the study.

Participant decision

- The participant requests to discontinue the study intervention.

Investigator decision

- The investigator decides that the participant should be discontinued from the study intervention.

Pregnancy

- The participant becomes pregnant during the study (see Section 8.3.5 and Section 10.4, Appendix 4).

Safety considerations

The participant:

- Has a malignancy (except for successfully treated basal or squamous cell skin carcinoma)
- Answered "yes" to Question 4 or Question 5 on the "Suicidal Ideation" portion of the C-SSRS
- Answered "yes" to any of the suicide-related behaviors on the Suicidal Behavior portion of the C-SSRS
A psychiatrist or appropriately trained professional may assist in the decision to discontinue the participant.
- Is diagnosed with LTBI during the study and are not a candidate for treatment as described in Section 7.1.1.1, or
- Has a serious or opportunistic infection that in the opinion of the investigator merits the study intervention being discontinued. Such infections may include, but are not limited to:
 - HIV/acquired immune deficiency syndrome (AIDS) infection
 - active TB infection or untreated LTBI (see Sections 7.1.1 and 8.2.6)
 - HCV RNA positive (Section 8.2.8)
 - HBV DNA positive (Section 8.2.7).

The participant should be referred to, evaluated and managed by a specialist physician with expertise in evaluation and management of viral hepatitis prior to discontinuation of any

immunomodulatory and/or immunosuppressive therapy, including study intervention. Timing of discontinuation from study intervention relative to the initiation of any antiviral treatment for hepatitis is to be based on the recommendation of the consulting specialist physician, in conjunction with the investigator, and aligned with medical guidelines and standard of care.

Hepatic event or liver test abnormality

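### Section 7.1.2 leaves stopping for HCV RNA and HBV DNA to investigator opinion where Sections 8.2.8 and 8.2.7 make it the rule, and Section 7.1.1.1 does not define a confirmed HBV DNA result

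*Protocol*

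**What the plan says.** **HCV RNA, and HBV DNA in general.** Among the safety reasons for permanent discontinuation, Protocol Section 7.1.2 has this scenario: "Has a serious or opportunistic infection that in the opinion of the investigator merits the study intervention being discontinued". A non-exhaustive list of examples follows. It includes HCV RNA positive, with a pointer to Section 8.2.8, and HBV DNA positive, with a pointer to Section 8.2.7 and no viral level.

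Section 8.2.8 says that study drug is permanently discontinued if HCV RNA is detected during the study, and states no exception. For HBV DNA above the limit of quantitation, Section 8.2.7 says "the participant will be permanently discontinued from the study intervention (see Section 7.1) and should be referred to a hepatology specialist immediately". It then adds: "In selected cases, investigators may temporarily continue study intervention in accordance with current immunomodulator management in the setting of HBV DNA positivity", to be considered in consultation with the sponsor.

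**HBV DNA below quantitation.** Section 7.1.1.1 requires drug to be withheld for "HBV DNA results reported as positive, or as detecting HBV DNA, but HBV DNA is below the level of quantification". Item 3 also asks for Medical Monitor contact about the participant's status and for a repeat test as soon as possible, and ends: "If HBV DNA is confirmed positive, then study intervention should be discontinued". For the same results the Section 8.2.7 table says, after one, "the test should be repeated within approximately 2 weeks" and, after two or more, "HBV DNA testing should be performed approximately once per month for the remainder of the study and referral to a hepatologist is recommended". These rows do not mention dosing.

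**The concern.** LY3462817 is intended to stimulate an immune inhibitory pathway, and participants who are anti-HBc positive but HBV DNA negative may be enrolled. Viral reactivation is the event this monitoring exists to catch, so the stopping rule should read the same wherever an investigator looks it up.

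It does not. Sections 8.2.7 and 8.2.8 state a stop and cite Section 7.1 for it. Section 7.1.2 then adds an opinion test and points back. An investigator working from 7.1.2, the section that lists the permanent stopping criteria, could take as discretionary what 8.2.8 makes mandatory for HCV RNA and 8.2.7 makes the default for quantifiable HBV DNA.

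The secondary gap is the undefined confirmation step. After two detectable, below-quantitation HBV DNA results, a site could stop drug because the repeat confirmed the first. It could also conclude that confirmation needs a quantifiable result and ask to restart.

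**Working it through.** The plan states no figure to reproduce. The main check sets the sections side by side.

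| Result on study | 7.1.1.1 item 3 | 8.2.7 or 8.2.8 | 7.1.2 |
|---|---|---|---|
| HBV DNA below quantitation, once | Withhold, contact Medical Monitor, repeat as soon as possible | Repeat within about 2 weeks; silent on dosing | Opinion-based, no level given |
| Repeat does not detect HBV DNA | No resumption rule in the item | Scheduled monitoring resumes; silent on dosing | Not triggered |
| HBV DNA below quantitation, two or more times | Stop if this counts as confirmation; otherwise still withheld | Monthly tests and referral; silent on dosing | Opinion-based, no level given |
| HBV DNA above quantitation | First-result trigger is limited to below quantitation | Permanent stop, with selected-case exception | Opinion-based, no level given |
| HCV RNA detected | Not covered | Permanent stop, no exception | Opinion-based |

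**Main point.** In the last two rows the sections differ in force. Section 7.1.2 opens by saying that discontinuation should occur in the listed scenarios, but this does not remove the difference, because the infection scenario itself contains the opinion test.

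**Secondary point.** Both readings of the third row are awkward.
- If a second below-quantitation result confirms, 7.1.1.1 stops drug at a level where 8.2.7 names no stop, and without the exception available at the higher level.
- If confirmation needs a quantifiable result, drug stays withheld and item 3 gives no criterion for ending the hold. Items 1 and 2 each address resumption; item 3 does not. What remains is the general sentence in Section 7.1.1: "The investigator should consult with the Medical Monitor and then determine when it is appropriate to recommence study treatment".

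**Infusions that depend on the reading.** The Schedule of Activities places infusions at Day 1 and Weeks 4, 8, 12, 16, 20 and 24, which makes 7. Scheduled on-treatment HBV DNA tests are at Weeks 12 and 24.
- Detection at Week 12 and again on the repeat: Weeks 16, 20 and 24 are at issue, 3 of 7. That is 3 × 300 = 900 mg or 3 × 700 = 2100 mg.
- First detection at Week 24, or no Period 2 dosing: 0.
- One detection, then a repeat that detects nothing: not counted. Withholding under 7.1.1.1 and retesting under 8.2.7 fit together, so any hold is the intended action.

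**Participants.** About 40 + 20 = 60 participants are randomized to LY3462817. The documents give none of the rates needed, so these are assumptions: anti-HBc prevalence 2% to 15%, share dosed in Period 2 20% to 40%, and a first detected result in 5% to 20% of those subject to the rule.
- Subject to the rule: 60 × 0.02 × 0.20 = 0.24, to 60 × 0.15 × 0.40 = 3.6.
- With a first detection: 0.24 × 0.05 = 0.012, to 3.6 × 0.20 = 0.72. Fewer have a second detection, which is the only disputed HBV case.

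**HCV.** Testing is scheduled only at screening. On-study results would come from unscheduled work, such as the comprehensive hepatic evaluation in Section 10.7.

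**The case against.** A reader might infer that 7.1.1.1 and 8.2.7 contradict each other, or that 8.2.7 allows dosing to continue through low-level HBV DNA. The documents do not support this. Section 8.2.7 is silent on dosing below quantitation, and silence does not override the mandatory withholding in 7.1.1.1. Monthly tests and referral can be done off drug, since 7.1.2 encourages participants who stop to remain in the study. If drug is stopped, both sections are followed. Item 3 also brings in the Medical Monitor while drug is withheld, which makes divergence between sites less likely. All of this stands, and it is why the HBV confirmation issue is secondary. The contact still supplies no criterion.

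The ordinary sense of confirmation is a repeat that again detects HBV DNA, and 8.2.7 equates HBV DNA negative with undetectable at screening. That favours one reading but does not define the term, and the 8.2.7 ladder, which ties its only stop to a quantifiable result, pulls the other way.

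On the main point, the 7.1.2 bullets refer directly to 8.2.7 and 8.2.8. The paragraph after them calls for specialist referral and bases the timing of discontinuation on specialist advice, which presupposes a stop. A careful investigator would probably reach the right answer. This lowers the risk, but the opinion test remains in the section that 8.2.7 and 8.2.8 cite as their authority.

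**Conclusion.** The point holds as a low-priority wording defect in safety rules. Section 7.1.2 is weaker than 8.2.8 for any detected HCV RNA, and weaker than 8.2.7 for HBV DNA above quantitation, where stopping is the default with a stated exception. Secondarily, 7.1.1.1 leaves open whether a second below-quantitation HBV DNA result is confirmation.

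The size is small: up to 3 Period 2 infusions for a participant with two detections, and an expected 0.01 to 0.7 participants with even a first. The participant figures rest wholly on the assumed rates above. It should not be inferred that the primary comparison is at risk. The first scheduled on-treatment test coincides with the Week 12 assessment, so scheduled testing does not affect the Week 12 primary endpoint.

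**What to change.** Three wording changes:

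1. **Section 7.1.2.** Take the two viral results out of the opinion-based list and give each its own bullet: *HCV RNA detected (Section 8.2.8)*, and *HBV DNA confirmed positive (Section 7.1.1.1) or above the limit of quantitation, subject to Section 8.2.7*. Keep the paragraph on specialist advice and timing.
2. **Section 7.1.1.1, item 3.** Define confirmation as a repeat test that again detects HBV DNA, at any level. State that drug may resume after Medical Monitor consultation if the repeat does not detect it.
3. **Section 8.2.7, below-quantitation rows.** Add *study intervention is withheld or discontinued per Section 7.1.1.1*.

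Do not extend the above-quantitation exception to below-quantitation results. It concerns temporarily continuing drug, whereas these participants already have drug withheld, so extending it would be a new clinical rule rather than a clarification.

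No tests are added, because the repeat and monthly HBV DNA tests are already in the protocol. The downside is that a very small number of anti-HBc-positive participants may lose up to 3 Period 2 infusions.
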